### **Subsequent anti-cancer therapy**

#### **Missing or partial start date of anti-cancer therapy after end of study treatment:**

- If the date has no missing year and month but the day is missing and if the date has same year and month with last dose date, then equal to last dose date+1, else 15th day of the month will be used.
- If the date has no missing year, but has missing month, and the year of last dose date is the same as the year of the start date, the date of last dose+1 will be used.
- If the date has no missing year, but has missing month, and the year of last dose is before the year of the start date, then July 1st will be used.
- If the start date is completely unknown, then use the date of last dose+1.

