### **Progression free survival (PFS)**

PFS is defined as the time (in months) from the date of first study medication to the earliest date of disease progression or death due to any reason whichever occurs first.

HMPL-523

PFS (months) = ([date of progression or death or censoring] - [date of first dose of study medication] + 1)/30.4375.

A patient is deemed to be censored according to the rules specified in **Error! Reference source not found.** below.

Error! Reference source not found.: **Progression-Free Survival Censoring Rules**

#	Situation	Date of Progression or Censoring	Outcome	Event/Censor reason
1	Death (without previously documented progressive disease [PD]) within two evaluable tumor assessments [a] from last evaluable tumor assessment or first dose (if no post-baseline tumor assessment)	Date of death	Event	Death
2	Death (without previously documented PD) after two or more consecutive missed/non-evaluable tumor assessments [a] from last evaluable tumor assessment or first dose (if no post-baseline tumor assessment)	Date of last evaluable tumor assessment or date of first dose (if no post-baseline tumor assessment)	Censored	Death after two or more consecutive missed or NE tumor assessments
3	Progression within two evaluable tumor assessments [a] from last evaluable tumor assessment or first dose (if no post-baseline tumor assessment before PD)	Date of progression	Event	Disease Progression
4	Progression after two or more consecutive missed/non-evaluable tumor assessments [a] from last evaluable tumor assessment or first dose (if no post-baseline tumor assessment before PD)	Date of last evaluable tumor assessment or date of first dose (if no post-baseline tumor assessment before PD)	Censored	Progression after two or more consecutive missed or NE tumor assessments
5	Progression after new anti-cancer treatment	Date of last evaluable tumor assessment before new anti-cancer treatment or date of first dose (if no post-baseline tumor assessment before new anti-cancer)	Censored	Progression after new anti-cancer therapy
6	No baseline tumor evaluable assessment and alive	Date of first dose	Censored	No baseline assessment
7	No post-baseline tumor evaluable assessment and alive	Date of first dose	Censored	No post-baseline assessment

HMPL-523

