- If the start date of new anti-cancer therapy is completely missing, then impute the date as

HMPL-523

last dose of study treatment + 1.

- If the start date of new anti-cancer therapy is partial, the imputation rules refer to [section 7.9](#).
- If new anti-cancer therapy is started without PD or is started prior to PD or death, the PFS will be censored at the date of the last evaluable tumor assessment no later than the date of initiation of new anti-cancer therapy (i.e. if an assessment occurs on the same day as the start of new anti-cancer therapy, the assessment will be used as it will be assumed the assessment occurred prior to the administration of new anti-cancer therapy).
- If a patient has only a baseline visit or does not have an assessment that is no later than the date of initiation of new anti-cancer therapy, the PFS will be censored at the date of first dose.

The median and quartiles for PFS and the PFS rates at 6 months, 12 months, together with their two-sided 95% confidence intervals will be estimated for each dose level (Stage 1) and malignancy type (Stage2) using the Kaplan-Meier method. The 95% CI for the median will be calculated from a log-log transformation based on the method by Brookmeyer and Crowley ([Brookmeyer, R., & Crowley, J. 1982](#)). Kaplan-Meier curves will be plotted.

Frequency and percentage for each type of event (PD or death) and censoring reasons will be presented as categories.

The PFS time or censoring time and the reasons for censoring will also be presented in a patient listing.

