### **Duration of response (DoR)**

Duration of response (DoR) is defined as the time from when the first response (CR, CRi, PR, nPR, VGPR, PR-L, and MR) was achieved until the earlier of the first documentation of definitive disease progression or death from any cause. If patients do not have disease progression or death, they will be censored following the same rules as for PFS. Only patients with response of CR, CRi, PR, nPR, VGPR, PR-L, or MR will be included in the analysis for DoR.

DoR (months) = ([date of first documentation of definitive PD or death from any cause] - [date of first response] + 1)/30.4375.

Percentages for the number of events/censorings of DoR will be calculated based on the number of responders.

Median DoR along with the two-sided 95% CI will be estimated using Kaplan-Meier method. The 95% CI for the median will be calculated using a log-log transformation based on

HMPL-523

Brookmeyer and Crowley (Brookmeyer, R., & Crowley, J. 1982) method. Kaplan-Meier curve will be plotted by dose level in Stage 1 and by the malignancy type in Stage 2.

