## 17.2. ADVERSE EVENTS

Treatment-emergent adverse events (TEAEs) are defined as AEs with an onset date on or after the first dose of study medication and no later than 30 days after the date of last study treatment administration or start of a new treatment of anti-neoplasm therapy, whichever is earlier. An exception is that study medication related SAE collected later than 30 days after the last treatment date or start of a new treatment of anti-neoplasm therapy will be treated as TEAEs.

Refer to [Section 7.9](#) for handling of partial dates for AEs. In the case where it is not possible to classify an AE as treatment-emergent or not, the AE will be classified as treatment-emergent.

An overall summary of AEs will include the number of patients with:

- Any AE
- Any TEAE
- Any TEAE of CTCAE Grade 3 or higher
- Any TEAE of CTCAE Grade 3
- Any TEAE of CTCAE Grade 4
- Any TEAE of CTCAE Grade 5
- Any Treatment Related TEAE
- Any Treatment Related TEAE of CTCAE Grade 3 or higher
- Any Treatment Related TEAE of CTCAE Grade 3

HMPL-523

- 
- Any Treatment Related TEAE of CTCAE Grade 4
  - Any Treatment Related TEAE of CTCAE Grade 5
  - Any Serious TEAE
  - Any Serious TEAE of CTCAE Grade 3 or higher
  - Any Serious TEAE of CTCAE Grade 3
  - Any Serious TEAE of CTCAE Grade 4
  - Any Serious TEAE of CTCAE Grade 5
  - Any Treatment Related Serious TEAE
  - Any Treatment Related Serious TEAE of CTCAE Grade 3 or higher
  - Any Treatment Related Serious TEAE of CTCAE Grade 3
  - Any Treatment Related Serious TEAE of CTCAE Grade 4
  - Any Treatment Related Serious TEAE of CTCAE Grade 5
  - Any TEAE Leading to Dose Reduction
  - Any TEAE Leading to Drug Interruption
  - Any TEAE Leading to Drug Discontinuation
  - Any TEAE Leading to Death
  - Any TEAE of Special Interest (AESI)

Listings will include the following:

- All AEs
- All SAEs
- AEs leading to Drug Discontinuation
- AEs Leading to Death
- All AESIs

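### An unknown or partly known start of new anticancer therapy is set to last dose + 1 without checking the documented progression date, so a real off-drug progression can be censored in PFS

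*SAP*

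**What the plan says.** SAP 7.9, under subsequent anti-cancer therapy, imputes the start date from the last dose or from a fixed calendar day:

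- Nothing known: "If the start date is completely unknown, then use the date of last dose+1".
- Month missing: where "the year of last dose date is the same as the year of the start date, the date of last dose+1 will be used". A last dose in an earlier year gives 1 July instead.
- Day missing: if year and month match the last dose, "then equal to last dose date+1, else 15th day of the month will be used".

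Note [b] to the PFS censoring table in SAP 16.1.1 repeats the first rule, beginning "If the start date of new anti-cancer therapy is completely missing, then impute the date as"; the imputed value is again the day after last dose, and for partial dates the note refers to 7.9.

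The imputed date then decides event or censoring. Row 5 of the table, "Progression after new anti-cancer treatment", censors at the last evaluable scan before the new therapy, or at first dose if there is none. Note [b] says the same: "If new anti-cancer therapy is started without PD or is started prior to PD or death, the PFS will be censored at the date". That date is the latest evaluable scan on or before therapy start. A scan on the same day as therapy start counts as before it. For DoR, patients without progression or death are handled as follows: "they will be censored following the same rules as for PFS".

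Start of new therapy also closes the TEAE window in SAP 17.2 (30 days after last dose "or start of a new treatment of anti-neoplasm therapy, whichever is earlier") and the on-treatment period in SAP 7.3 (37 days, with the same cut).

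**The concern.** New therapy often follows progression, yet none of these rules compares the imputed start with a documented PD. Neighbouring rules in SAP 7.9 do bound imputed dates by known ones: death by the last known alive date and the end of study, last dose by the end of study, and diagnosis by the consent date. The date that switches a PFS event to a censoring has no such check.

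The situation can arise by design. Protocol 5.6.12 and 5.7.1 keep patients who stop drug for reasons other than progression on study, with quarterly scans until first progression, new therapy, death or 12 months from first dose. A scan is also due at termination for such reasons. Progression in these patients is found after the last dose.

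At stake is PFS, an efficacy measure for the Stage 2 primary objective. It is reported by malignancy in small cohorts: HL 25, PTCL 9, CLL post-BTK 7 and the others 0 to 2 (Protocol Table 2). One lost event is 1/25 = 4% of HL, 1/9 = 11% of PTCL and 1/7 = 14% of CLL post-BTK.

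**Working it through.** The plan states no figure on this point, so the check is on date logic, followed by an illustration of size.

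**When an event flips.** PD stays an event if PD date ≤ imputed therapy start, because a same-day scan counts as before therapy. With imputed start = last dose + 1, every PD at last dose + 2 or later is censored, whatever the true order.

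**Dated cases.** These use first dose 3 January 2022, a week-8 scan on 28 February, and PFS = (date − first dose + 1)/30.4375. The dates are invented; the rules are those of the SAP.

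| Case | Last dose | PD | True start | What is recorded | Imputed start | SAP result | Result with true start |
|---|---|---|---|---|---|---|---|
| A | 12 Apr | 25 Apr | 5 May | nothing, or year only | 13 Apr | censored 57/30.4375 = 1.87 months | event 113/30.4375 = 3.71 months |
| B | 28 Apr | 25 Apr | after PD | nothing | 29 Apr | event 3.71 | event 3.71 |
| C | 10 Mar | 20 Apr | 27 Apr | April | 15 Apr | censored 1.87 | event 108/30.4375 = 3.55 |
| D | 10 Mar | 12 Apr | 5 Apr | April | 15 Apr | event 100/30.4375 = 3.29 | censored 1.87 |

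Case A is the defect. If the month (May) had been recorded in case A, the imputed start would be 15 May and PD would remain an event. Case B shows that PD on or before last dose + 1 is safe. Cases C and D show that the 15th rule can err in either direction; the 1 July rule has the same property.

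**With the fix.** In case A, the later of 13 April and 26 April is 26 April, so PD is an event at 3.71 months. In case C, the later of 15 April and 21 April is 21 April, still within the recorded month, so PD is an event at 3.55 months. Case D is unchanged.

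**Size, under assumptions.** Inputs: n = 25 (HL); exponential PFS with true median 8.2 months (the expansion-stage median of the China study in Protocol 2.2.4.4) or 4 months (a second assumption); scans at weeks 8, 16 and 24, then every 12 weeks; all patients progress. In k patients chosen at random, the event becomes a censoring at the previous scan (56 or 84 days earlier) or, if there is none, at first dose. There were 2,000 replicates per setting.

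| k | Mean KM median, true 8.2 | 6-month PFS | Mean KM median, true 4 | 6-month PFS |
|---|---|---|---|---|
| 0 | 9.81 | 62.9% | 5.14 | 38.4% |
| 1 | 10.22 | 64.1% | 5.27 | 39.7% |
| 3 | 10.93 | 65.8% | 5.60 | 42.2% |
| 5 | 11.69 | 68.5% | 6.09 | 45.1% |

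The k = 0 medians exceed the true values because progression is dated at the scan that finds it. One lost event adds 10.22 − 9.81 = 0.41 or 5.27 − 5.14 = 0.13 months. Five add 11.69 − 9.81 = 1.88 or 6.09 − 5.14 = 0.95 months.

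**Safety windows.** If last dose + 1 were also used in SAP 17.2 and 7.3, the time after last dose would shrink from 30 days to 1 (TEAE) and from 37 days to 1 (on-treatment).

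**The case against.** The exposed group is narrow. Progression requires stopping drug (Protocol 5.7.3), and the termination scan is for patients who stopped for other reasons. Those whose PD was found on treatment are unaffected. The same-month branch is narrower still: last dose, PD and therapy start must all fall in one calendar month. The documents do not support saying that PD is often first documented after last dose. All of this stands and limits the reach, but it leaves the unknown-date and year-only branches open.

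The study is descriptive, no test of PFS is planned, and censoring reasons are tabulated and listed by patient. Affected cases could therefore be found. That lowers the severity; it does not correct the estimate.

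The fix presumes that therapy followed PD when the record is silent. That is true, but the present rule presumes the opposite without looking at the PD date.

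Four stronger readings are tempting and are not supported:

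- *The error always favours the drug.* This holds for the last dose + 1 branches only; case D goes the other way.
- *ORR is inflated because the false date also closes the best-response window.* Losing a later PD cannot improve a response already recorded. A patient left with no evaluable scan becomes NE, which SAP 16.1.1 counts as a non-responder.
- *Adverse events certainly leave the TEAE tables.* The SAP ties this imputation explicitly only to PFS. SAP 17.2 keeps late drug-related SAEs as TEAEs and classes events that cannot be assigned as treatment-emergent. The any-AE count and the full listing are not cut.
- *Many events are lost.* A reader might multiply generous shares, such as 25 × 0.5 × 0.5 = 6.25. That treats every off-drug PD as followed by new therapy and every incomplete date as flipping an event, which the 15th and 1 July rules contradict.

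**Conclusion.** The concern holds for PFS in a defined group: patients who stopped drug for a reason other than progression, had PD documented at least two days after last dose, and then started new therapy whose start is unknown or known only to the year or month of the last dose. For them a real event becomes a censoring at an earlier scan, which biases PFS upward. DoR is exposed to the same extent only if its reference to the PFS rules includes row 5; read literally, that sentence covers patients without progression or death.

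The number of such patients is not given and may be zero. The shifts of 0.13 to 1.88 months in the median are illustrations for one to five lost events among 25, not estimates for this trial.

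The adverse-event question is separate and conditional. It arises from the last dose + 1 rule itself, not from ignoring PD, and only if the imputed date is used for those windows. In that case, AEs from about day 2 after last dose, other than drug-related SAEs, would leave the TEAE tables. The SAP should say which rule prevails. Overall: should-fix.

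**What to change.** Before database lock, which SAP Section 2 allows:

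1. In SAP 7.9 and PFS note [b], add for PFS and DoR: where PD is documented and the therapy start is imputed, use the later of the present imputed date and PD date + 1, as far as the recorded year and month allow. Otherwise keep the present rule. If PD falls on the last day of the recorded month, stop at that day; the same-day provision then keeps PD as an event. If the recorded parts show that therapy came before PD, the censoring stands.
2. In the DoR paragraph, say whether row 5 applies.
3. In SAP 7.3 and 17.2, state that an imputed therapy start does not shorten the 37-day or 30-day window unless the known date parts prove that therapy began earlier.

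A PFS sensitivity analysis that ignores censoring for new therapy would show whether the choice matters; it is useful but optional.

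The cost is a few sentences and a small derivation change. One therapy may carry different dates for efficacy and safety, which the dataset specification should record. PFS may become slightly less favourable. Deciding now avoids a choice made after its effect on PFS is known.

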### **Birth Date**

#### **Missing or partial birth date:**

- If only year is present, July 1st will be used to impute the birth date.
- If only year and month is present, 15 will be used to impute the birth date.

### **Oncology Diagnosis History Dates**

- If year is missing, do not impute.
- if year and month are known but the day is unknown, day will be imputed as 15.
- If only year is known, month and day would be imputed as July 1st.

Note: The imputed date will be compared to inform consent date. If it is later than the inform consent date, the incomplete date will be imputed as the inform consent date.

## **8. OUTPUT PRESENTATIONS**

Summary results will be presented by Stage 1 and Stage 2. For Stage 1, summary will be by dose level. For Stage 2, summary will be by type of malignancies and overall. Some of the efficacy summary results for Stage 1 may be presented by type of malignancy for any interim looks.

HMPL-523

---

## 9. DISPOSITION AND WITHDRAWALS

All patients who provided informed consent will be accounted for in this study.

### 9.1. DISPOSITION

Patient disposition, discontinuation as well as reasons for discontinuation will be presented for the all enrolled set. The number of patients who provided informed consent for the study will be summarized. Screen failed patients and the reason for screen failure as well as patients who passed screening but withdrew before study treatment will also be summarized.

The number and percentage of patients who completed, discontinued or were still on the treatment will be presented. Reasons for discontinuation from study treatment as recorded on the “End of Treatment (EOT)” form will be summarized. The number and percentage of patients who have completed, discontinued or were still on study will be presented. Reasons for discontinuation from study as recorded on “End of Study (EOS)” form will be summarized. The follow up time will be also summarized with mean, median, and standard deviation.

Follow up time (days) = the latest date in database – the first dose date + 1. For the interim evaluation of Stage 1 results, follow-up time (days) is defined as date of cutoff (even if patient was off treatment or died after the cutoff date) – first dose date +1.

In addition, number and percentage of patients with <6, >=6, <12, >=12 months follow-up time will be summarized.

The number/percentage of patients included in FAS, RES, DEAS (stage 1 only), and PKAS will be summarized for both Stage 1 and Stage 2. A by-patient listing will include the inclusion/exclusion of patients in each analysis set.

Individual listings containing the site and patient number, informed consent information, first and last study medication administration date, treatment discontinuation information and end of study information will be provided separately for Stage 1 and Stage 2. A separate data listing will include eligibility for study entry based on inclusion/exclusion criteria.

### 9.2. PROTOCOL DEVIATIONS

Protocol deviations will be collected by the clinical team and entered into the clinical trial management system (CTMS). The study team will discuss, identify and classify the important eligibility criteria or post-entry deviations from operational team monitor reports before final data base lock. A summary table for protocol deviations by major deviation category will be presented. Major protocol deviations related to study inclusion or exclusion criteria, conduct of the trial, patient

HMPL-523

management, or patient assessment will be also listed for FAS. The protocol deviation listing will present deviation category, deviation term, deviation date, severity (major/minor), and actions taken.

COVID-19 Visit Impact to planned visit will be included in by-patient listings.

## 10. DEMOGRAPHIC AND OTHER BASELINE CHARACTERISTICS

Demographics and other baseline characteristics will be presented for the FAS.

Continuous demographic variables: age, height, weight, and body mass index will be summarized using descriptive statistics (mean, standard deviation, median, minimum, and maximum). For all the other categorical variables, results will be presented as number and percentage of patients.

The following demographic and baseline characteristics will be reported for this study:

- Age (years) = floor ((date of informed consent-date of birth+1)/365.25)
- Age Category:
  - <65 years
  - ≥65 years
- Gender (including childbearing potential for female patients)
- Race
- Ethnicity
- Weight at Baseline (kg)
- Height at Baseline (cm)
- BMI (kg/m^2) at Baseline = weight(kg) \*10000/(height(m)\*height(m))
- Alcohol Use
- Drug Abuse
- Tobacco Use
- Baseline Eastern Cooperative Oncology Group (ECOG) Performance Status
  - 0
  - 1
  - >1
- Baseline LVEF (%)
- Initial Tumor Type (CLL, SLL, MCL, FL, WM/LPL, MZL, PTCL, CBCL, DLBCL) and sub-

HMPL-523

types for MZL, and PTCL, and prior BTK inhibitor exposure for CLL/SLL only.

- B-symptoms
  - Unexplained weight loss  $\geq 10\%$  over previous 6 months (Yes, No, Unknown)
  - Fever  $> 38\text{ C}/100.5\text{ F}$  for 2 or more weeks without other evidence of infection (Yes, No, Unknown)
  - Night sweats for more than 1 month without evidence of infection (Yes, No, Unknown)
- Bone Marrow Involvement by PET-CT
- Bone Marrow by Biopsy
- Bone Marrow by Aspirate
- Serum Beta 2-Microglobulin
- Viral Serology
- Serum Immunoglobulin
- Leukocyte Immunophenotyping
- 17p del/TP53 Mutation Status

## 11. OTHER BASELINE DISEASE CHARACTERISTICS

Prior cancer diagnosis includes tumor type, immunohistochemistry, flow cytometry, other pathological findings, prior anti-neoplastic therapies and procedures and related outcome. FAS will be used to summarize baseline disease characteristics. Results will be displayed by dose level for stage 1 and by types of malignancy for stage 2.

The disease related baseline characteristics will be summarized by the type of malignancy as following:

- Time since diagnosis (months) calculated as (date of first dose date – date of primary diagnosis + 1)/30.4375
  - Initial Immunohistochemistry, Flow Cytometry and other Pathological Findings
  - Rai stage (only for patients with lymphoma type CLL)
  - Binet stage (only for patients with lymphoma type CLL)
- Ann Arbor Staging at study entry (for patients with lymphoma other than CLL)
- Risk Groups
  - For CLL/SLL/MZL: Low, Low-intermediate, High-Intermediate, High from “Diffuse Lymphoma International Prognostic Index” CRF page
  - For FL: Low, Intermediate, High from “Follicular Lymphoma International

HMPL-523

- Prognostic Index” CRF page
- For MCL: Low, Intermediate, High from “Simplified Mantel Cell Lymphoma International Prognostic Index (MIPI) Score” CRF page
- For WM/LPL: Low, Intermediate, High from “International Prognostic Scoring System for Waldenstrom’s Macroglobulinemia (ISSWM)” CRF page

